| Approximate daily blood draw, mL                                                     |           | 86                  |                | 86                        | 26                        | 86                        | 86                        | 86                                 |                   | 86                        | 26                        | 86                        | 86                        | 86              | 86              | 86              | 86              | 86                      |
| Approximate cumulative study blood draw, mL                                          |           | 86                  | 86             | 172                       | 198                       | 284                       | 370                       | 456                                | 456               | 542                       | 568                       | 654                       | 740                       | 826             | 912             | 998             | 1,084           |                         |

AE adverse event; AESI adverse event of special interest; d day; m month; SAE serious adverse event; Vac vaccination

① pre vaccination; ② pre and post vaccination; ③ blood samples for immunogenicity will only be taken if the early exit visit is at least 14 days after the previous immunogenicity blood draw; ④ if the early exit visit is within 7 days after vaccination; ⑤ if the early exit visit is within 28 days after vaccination.

\* Timing of revaccination to be defined based on Ad26/protein preF RSV vaccine clinical data (Studies VAC18193RSV1004, VAC18193RSV2001, and VAC18193RSV3001). In case revaccination will be later than 12 months relative to the first dose, additional blood sampling 1 year post first vaccination may be included.

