### Expanded Safety Cohort (Cohort 3)

In the expanded safety cohort, approximately 400 participants will be randomized in parallel to 1 of 5 arms (in a 6:3:3:2:2 ratio to Arms 10, 11a, 11b, 12, and 13; [Table 7](#)). No pauses in enrollment for safety assessments are planned. Participants will receive either the selected 2×1 mL formulation based on the results from Cohorts 1 and 2, the selected 1 mL formulation for future clinical development, placebo, or the current Ad26/protein preF RSV vaccine (1×10^11 vp Ad26.RSV-A.preF/150 µg RSV-A preF protein).

Vaccine components evaluated in Cohorts 1 and 2 will be administered as 2 IM injections of 1 mL in the same deltoid muscle. However, once the optimal composition is selected, manufacturing formulation will be adjusted to ensure the administration of a single 1 mL vaccine dose in subsequent cohorts. Participants in Arms 11a and 11b will receive the selected vaccine in a 1 mL formulation and a second injection with placebo (1 mL) for blinding purposes. Cohort 3 thus will compare the 2×1 mL formulation of the selected combination of RSV vaccine components from Cohorts 1 and 2 (Arm 10) with the 1 mL formulation to be used for future clinical development (Arms 11a and 11b) with follow-up for 1 year post-vaccination in a double-blind placebo-controlled fashion. Participants in Arm 13 will receive the current Ad26/protein preF RSV vaccine (1×10^11 vp Ad26.RSV-A.preF/150 µg RSV-A preF protein) in a 1 mL formulation and a second injection with placebo (1 mL) for blinding purposes. Participants in Arms 11a, 11b and 12 will continue the study to assess durability and the effect of revaccination with follow-up up to 5 years post first vaccination. The timing of revaccination (at least 12 months relative to the first dose) will be based on Ad26/protein preF RSV vaccine clinical data.

For a subset of the participants, additional cellular immunogenicity assessments will be performed. This subset will be referred to as the Cellular Immuno Subset and will consist of approximately 240 participants: 40 participants per arm in Arms 10, 12 and 13, and 60 participants per arm in Arms 11a and 11b. The Cellular Immuno Subset will be recruited in study sites that have PBMC collection capability.

VAC18195 (JNJ 64400141/ JNJ 64213175/ JNJ-86051823/ JNJ 78991172)

Clinical Protocol VAC18195RSV1001 Original

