| Chemokine/cytokine analysis                                                 | Levels of chemokines and cytokines in serum                                                                                                                                                                                                                                                                                                                                                                       |
| Sequencing of T-cells and/or B-cells                                        | Including but not limited to sequencing of TCR and BCR including VH/VL (heavy/light chain) characterization                                                                                                                                                                                                                                                                                                       |

\* Analysis of neutralizing antibodies against the RSV A2 and RSV B strain is a primary endpoint in the vaccine components selection cohort (Cohorts 1 and 2) and in the revaccination and durability cohort (Cohort 4), and a secondary endpoint in the expanded safety cohort objective (Cohort 3).

\*\* Only applicable for participants with blood draws for cellular responses.

ADCC: antibody dependent cell mediated cytotoxicity; ADCP: antibody dependent cell mediated phagocytosis; BCR: B cell receptor; ELISA: enzyme linked immunosorbent assay; ELISpot: enzyme linked immunospot; F: fusion; ICS: intracellular cytokine staining; IFN  $\gamma$ : interferon gamma; IL 2: interleukin 2, Ig: immunoglobulin; PBMC: peripheral blood mononuclear cell; RSV: respiratory syncytial virus; TCR: T cell receptor; VH: heavy chain variable domain; VL: light chain variable domain; VNA: virus neutralizing antibody

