##### **9.4.3. Immunogenicity Analyses**

Immunogenicity data of corresponding arms from Cohort 1 and Cohort 2 will be combined in all analyses. Immunogenicity data of corresponding arms from Cohort 3 and Cohort 4 will be combined as applicable.

Continuous variables will be summarized descriptively. For continuous parameters, descriptive statistics of the actual values will be calculated at all timepoints, including geometric mean with 95% CI, median and quartiles, as applicable. Additionally, geometric mean fold rises from baseline and corresponding 95% CIs might be calculated.

For combined primary endpoint data of Cohort 1 and Cohort 2, geometric mean ratios between each active arm and Arm 1b will be calculated at all available timepoints, with corresponding 95% CI, as applicable. For Cohort 3, Arms 11a and 11b will be combined and the active arms will be compared to each other at all available timepoints up to 1 year after vaccination on Day 1, by means of geometric mean ratios with corresponding 95% CI. For durability and revaccination evaluation Arm 11a (Cohort 3) and Arm 14 (Cohort 4) will be combined, Arm 11b (Cohort 3) and Arm 15 (Cohort 4) will be combined, and Arm 12 (Cohort 3) and Arm 16 (Cohort 4) will be combined.

For immunogenicity analyses, baseline is considered as the last assessment pre-vaccination. Graphical representations of immunologic parameters will be made as applicable.

Geometric means per arm, and geometric mean ratios between active arms, with corresponding 95% CIs will be estimated via an analysis of variance (ANOVA) including all active arms, using log-transformed post-vaccination immune parameter response as dependent variable and study arm as independent variable. The means and differences in mean and CIs will be back-transformed (by exponentiation) to CIs around a GMT or geometric mean titer ratio (GMR). This analysis will be performed for all available assays and all time points, separately per assay. Data of the same arms from different cohorts will be combined, as applicable.

As a sensitivity analysis, the ANOVA may also be performed adjusting for the respective baseline titers, by including baseline titer as additional covariate.

For categorical variables, frequency tables will be presented.

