### 5.1.3. Immunogenicity Visit Windows

For the immunogenicity analysis, assessments will be allocated to an analysis visit based on the planned visit as captured in the CRF. Visits that are out of the protocol-defined visit windows (see the table below) will not be included in the per-protocol immunogenicity analysis. However, they may be included in sensitivity analyses.

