#### 5.3.3. Analysis Methods for the Primary Immunogenicity endpoint(s)

For Cohort 1, 2 and 4 the primary endpoint will be RSV neutralization antibody titers measured for RSV-A and RSV-B. In Cohort 3, RSV neutralization antibody titers are a secondary endpoint.

Data of corresponding arms from Cohort 1 and Cohort 2 will be combined in all analyses. Immunogenicity data of corresponding arms from Cohort 3 and Cohort 4 will be combined as applicable, too.

Descriptive statistics will be used for all arms to analyze the actual values (geometric mean, 95% CI, minimum, maximum, median and quartiles) and fold increase from baseline at all timepoints, as well as the percentage of participants with 2- and 4-fold increases from baseline. Additionally, the RSV-A/RSV-B antibody ratio will be reported by time points and the fold increase of RSV-A/RSV-B antibody ratio from baselines will be calculated at all timepoints.

For combined data from Cohort 1 and Cohort 2, geometric mean ratios for each active arm relatively to control Arm 1a and relatively to control Arm 1b, as well as relatively to each other will be calculated at all available timepoints along with corresponding 95% CI as applicable.

For Cohort 3, Arms 11a and 11b will be combined and the active arms (10, 11a+11b, 13) will be compared to each other at all available timepoints up to 1 year after vaccination on Day 1 by calculating the geometric mean ratios along with corresponding 95% CIs.

For durability and revaccination evaluation analyses, the following arms will be combined and compared to each other for all timepoints:

- Arm 11a (Cohort 3) combined with Arm 14 (Cohort 4);
- Arm 11b (Cohort 3) combined with Arm 15 (Cohort 4);
- Arm 12 (Cohort 3) combined with Arm 16 (Cohort 4).

Geometric means per arm of values for RSV-A, RSV-B and the ratio of RSV-A/RSV-B, geometric mean ratios for RSV-A, RSV-B and the ratio of RSV-A/RSV-B between all active arms along with corresponding 95% CIs will be estimated via an analysis of variance (ANOVA) using log-transformed post-vaccination immuno parameter response as dependent variable and study arm as independent variable. The means and differences in mean and CIs will be back transformed (by exponentiation) to CIs around a geometric mean or geometric mean ratio. This analysis will be performed by time points, separately per parameter. As a sensitivity analysis, the ANOVA may also be performed adjusting for baseline titer, age and sex.

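### If revaccination is set later than 12 months, Arms 11a and 11b have no required 1-year sample, so the planned 1-year titre contrasts with them can drop out

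*Protocol*

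**What the plan says.** **The comparison.** Protocol 4.1 says that Cohort 3 compares Arm 10 with Arms 11a and 11b "with follow-up for 1 year post-vaccination in a double-blind placebo-controlled fashion". Protocol 9.4.3 pools 11a with 11b and states that "the active arms will be compared to each other at all available timepoints up to 1 year after vaccination on Day 1", using geometric mean ratios with 95% CIs. SAP 5.3.3 names the groups (10, 11a+11b, 13), to be "compared to each other at all available timepoints up to 1 year after vaccination on Day 1". The footnote to Protocol Table 12 makes these titres "a secondary endpoint in the expanded safety cohort objective (Cohort 3").

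**The samples.** Protocol 1.3.2 and Table 10 give Arms 10 and 13 a Day 365 visit, after which these arms are complete. Protocol 1.3.3 and Table 11 take Arms 11a, 11b and 12 from Day 183 straight to Day X. Protocol 4.1 sets a lower bound only: "The timing of revaccination (at least 12 months relative to the first dose"). If Day X falls later than 12 months, the footnote in Protocol 1.3.3 says that "additional blood sampling 1 year post first vaccination may be included".

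**The analysis visits.** Under SAP 5.1.3, "assessments will be allocated to an analysis visit based on the planned visit as captured in the CRF", and "Visits that are out of the protocol-defined visit windows (see the table below) will not be included in the per-protocol immunogenicity analysis". SAP Table 4 has a Day 365 row with window [335, 395] for Arms 10 and 13. The block for Arms 11a, 11b, 12 and Cohort 4 has a Day X row with window [X−30, X+30] and no Day 365 row.

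**The AESI interval.** In SAP 5.3.2.3, the 57-day to 6-month interval after dose 2 ends at the later of dose 2 + 183 days and a Day 547 visit, subject to last contact and data cut-off. SAP Table 3 instead refers to the scheduled visit 182 days after vaccination.

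**The concern.** One year is the stated length of the comparison between the two formulations, but the schedule secures a 1-year sample on one side only. If Day X is moved beyond 12 months, whether Arms 11a and 11b are sampled at 1 year is left to a later decision. If the answer is no, the 1-year ratio of the 1 mL to the 2×1 mL formulation cannot be estimated. The plan's qualifier about available timepoints would let it disappear without any recorded departure from the plan. An analysis plan can be amended later; a blood sample that was not taken at 1 year cannot be recovered.

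If the optional sample is taken, the SAP as it stands has no analysis visit to put it in. The fixed Day 547 reference is a related weakness: it is a rule written as if Day X were already known.

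**Working it through.** **1. Windows at X = 365.** SAP Table 4 uses the target day ± 30. For Day 365: 365 − 30 = 335 and 365 + 30 = 395, which reproduces [335, 395]. For Day X at X = 365 the row gives the same [335, 395], counted from the same reference day (vaccination 1). In that case nothing is lost.

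**2. Required samples up to 1 year when X is later than 12 months.**

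| Arms | Required post-vaccination samples up to 1 year | Next sample |
|---|---|---|
| 10, 13 | Days 15, 29, 85, 183, 365 | none; arms completed |
| 11a, 11b | Days 15, 29, 85, 183 | Day X |

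The last required common timepoint is Day 183. One of five timepoints is affected.

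**3. Contrasts.** Three active groups give 3 × 2 / 2 = 3 pairwise ratios. Two involve 11a+11b: 10 vs 11a+11b and 13 vs 11a+11b. The pooled group has 75 + 75 = 150 participants, against 150 in Arm 10 and 50 in Arm 13. Only 10 vs 13 is secured at 1 year for every X.

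**4. Possible substitutes.** Arms 10 and 13 have no sample after Day 365 that could be set against a later Day X. The Day X sample of 11a+11b belongs to a different planned visit, and SAP 5.1.3 assigns samples by planned visit.

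**5. Is a 1-year draw already budgeted?** Protocol section 8 gives 364 mL for participants without cellular sampling in these arms: 14 draws × 26 mL = 364. For the cellular subset, 12 × 86 + 2 × 26 = 1,084 mL, as stated. Neither total contains a Day 365 draw in addition to Day X.

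**6. AESI interval.** 365 + 182 = 547, so the Day 547 visit is the 6-month post-dose-2 visit only when X = 365. For another X no such visit exists and the interval ends at dose 2 + 183 days. The 6-month visit has a window of ± 14 days, so a late visit that is still in window can fall at 182 + 14 = 196 days after dose 2. The shortfall is up to 196 − 183 = 13 days per participant.

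**The case against.** There is a fair case that little needs doing.

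- *The protocol foresees this.* The footnote names both the trigger and the remedy, and X is open on purpose because it depends on data from other studies. That stands. What remains is that the remedy is optional although the comparison it serves is stated.
- *Up to 1 year is an upper bound.* Read with the qualifier about available timepoints, neither document promises a Day 365 ratio. That stands too, so the plan does not contradict itself. Protocol 4.1 nevertheless gives 1 year as the follow-up for this comparison.
- *X = 365 looks like the SAP's working assumption.* The Day 547 reference supports this, which makes the loss less likely. The protocol and SAP Table 4 still leave X open.
- *The SAP is version 1.0 and can be updated.* A row for a visit not yet scheduled is not an omission in itself. Agreed: the missing row is easily repaired before analysis. The missing draw is not.
- *The AESI rule still covers at least 183 days* for a participant who stays in follow-up, and events after that are moved to a later interval, not discarded. Agreed.

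Two stronger readings are tempting. A reader might compare the Day X window with [335, 395], see that they share no day once X − 30 exceeds 395 (from X = 426), and infer that the contrast survives up to that day and fails after it. The documents do not support this. Samples are allocated by planned visit, and the windows only decide whether a sample stays in the per-protocol analysis, so Day 426 is not a threshold in the plan. The relevant condition is whether the planned X is later than 12 months.

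A reader might also infer damage to Cohort 4, where titres are primary. Its three arms share one schedule and keep the pre-dose Day X sample and the yearly samples, and Arm 10 is not among its durability comparisons.

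**Conclusion.** The concern holds in a conditional and limited form. If X is set later than 12 months and the optional draw is not taken, two of the three 1-year titre contrasts in Cohort 3 are lost, including the randomised comparison of the two formulations. If the draw is taken, the current SAP has no row for it. The contrasts at Days 15, 29, 85 and 183 are unaffected, no hypothesis is tested, and the endpoint is secondary in this cohort. At X = 365 nothing is lost. The documents do not show that X will be late, so it would be wrong to say that the 1-year comparison will fail.

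The AESI wording is a separate small correction: up to 13 days per participant, and only if X differs from 365. The 13 days use the visit timing in Protocol 1.3.3 (X+182); Protocol Table 11 lists the same visit as X+183. Overall this is a minor point, worth acting on because the draw cannot be made up afterwards.

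**What to change.** 1. **Protocol 1.3.3, footnote on revaccination timing.** If the planned X is later than 12 months, state that one 26 mL humoral sample *will* be drawn at Day 365 in Arms 11a, 11b and 12. Arm 12 is included because a draw in 11a and 11b alone would show sites who had received placebo, and Protocol 6.3 undertakes to preserve the blind across these three arms. Allow no exemption when X is only slightly later: at Day 365 a site cannot know when the Day X sample will in fact be taken.
2. **SAP Table 4.** Add a Day 365 row with window [335, 395] for these arms, and state that when X = Day 365 the pre-dose Day X sample serves as the Day 365 sample.
3. **SAP 5.3.2.3.** Replace the Day 547 visit with the scheduled visit 182 days after vaccination 2, in line with SAP Table 3.

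**Cost.** Items 2 and 3 are wording only. Item 1 costs something only if X is later than 12 months: one extra visit and 26 mL for up to 75 + 75 + 50 = 200 participants. Of these, 60 + 60 + 40 = 160 are in the cellular subset (1,084 + 26 = 1,110 mL over 5 years) and 200 − 160 = 40 are not (364 + 26 = 390 mL). Without a cellular draw there would be no 1-year cellular comparison with Arm 10; that endpoint is exploratory in Cohort 3.

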**Table footnotes for all cohorts:**

- a. For visits more than 3 months apart, sites will be encouraged to make quarterly phone calls prior to the indicated visit timing to ensure participant engagement.
- b. Safety only visits will be by telephone (Cohorts 3 and 4).
- c. An early exit visit will be conducted as soon as possible for those participants who are unable to continue participation in the study, for whom consent is not withdrawn. Participants who wish to withdraw consent from participation in the study will be offered an early exit visit (prior to formal withdrawal of consent).
- d. In addition, sentinel participants will be contacted by telephone 24 hours post-dose to collect safety information.
- e. Signing of the ICF should be done before any study-related activity.
- f. Medical history of all participants will be recorded in the eCRF, including whether each condition places the participant at increased risk for severe RSV disease. The conditions placing a participant at increased risk of severe RSV disease include congestive heart failure, coronary artery disease (such as angina pectoris, ischemic cardiomyopathy, history of myocardial infarct, or history of coronary artery bypass graft or coronary artery stent), and chronic lung disease (such as asthma and chronic obstructive pulmonary disease). Baseline information on risk factors for thrombosis and/or thrombocytopenia should also be recorded, as well as history of past COVID-19 infection.
- g. Prestudy therapies administered up to 30 days pre-vaccination must be recorded on Day 1.
- h. A physical examination, including height and body weight, will be carried out on Day 1. At all other visits, an abbreviated, symptom-directed examination will be performed if deemed necessary by the investigator based on any clinically relevant issues, clinically relevant symptoms, and medical history.
- i. Sitting systolic and diastolic blood pressure, heart rate, and respiratory rate after at least 5 minutes rest on Day 1. At non-vaccination visits, vital signs will be measured if deemed necessary by the investigator.
- j. Investigator must check for clinically significant acute illness at the time of vaccination or body temperature of  $\geq 38.0^{\circ}\text{C}$  ( $\geq 100.4^{\circ}\text{F}$ ) within 24 hours prior to the planned time of vaccination. In such cases, the participant may be vaccinated up to, and no later than 10 days after the scheduled vaccination, or be withdrawn at the discretion of the investigator.
- k. Blood sample volumes are approximate. Refer to the laboratory manual for additional details.
- l. Aliquots of serum samples collected for immunogenicity test can be reconverted for participant's safety purposes upon sponsor request. Please refer to [Appendix 2](#) for a non-exhaustive list of tests that will be requested on these samples in case of potential AESI reporting.
- m. Blood for humoral immune responses will be drawn from all participants. Blood for cellular immune responses will be drawn from a subset of participants (from Cohorts 1, 2, and 3; not applicable to Cohort 4).
- n. Based on results available at the time of primary analysis, the sponsor will decide which arms will continue with blood sampling for cellular immune responses beyond 6 months post vaccination in Cohorts 1 and 2.
- o. After vaccination, participants will remain under observation at the study site for at least 30 minutes for presence of any acute reactions and solicited events. Any unsolicited AEs, solicited local (injection site) or systemic AEs, and vital signs (sitting systolic and diastolic blood pressure, heart rate, and respiratory rate after at least 5 minutes rest, and body temperature) will be documented by the study site personnel following this observation period.
- p. All (S)AEs and special reporting situations related to study procedures or to non-investigational (concomitant) Janssen products will be collected from ICF signature onwards until the end of the study for all participants. All other SAEs and AESIs will be collected from administration of study vaccine (Day 1) until 6 months after the last study vaccination. AEs leading to discontinuation from vaccination and/or study will be collected for the duration of the study.
- q. AESIs, including potential AESIs, are to be reported from the moment of vaccination until 6 months after the last study vaccination.
- r. Concomitant therapies will be collected from the time of study vaccination through 28 days post-vaccination when associated with an AE, and from ICF signature until 6 months after the last study vaccination when associated with an SAE or AESI.
- s. Any history of SARS-CoV-2 vaccination (name/manufacturer of the vaccine and date of administration, whenever possible) prior to and during the study will be collected in the eCRF.
- t. All COVID-19 cases will be collected for all participants for the duration of the study. COVID-19 cases reported by the participant will be reported in the eCRF by the investigator.

- u. Rulers and thermometers will be distributed at these visits.
- v. Participants will be contacted by telephone 2 to 4 days post-vaccination to remind them to fill in the participant diaries and to check that they are entering information correctly.

